##### **12.2.1.2. Serious Adverse Event**

An SAE is any AE occurring at any dose and regardless of causality that:

- Results in death
- Is life-threatening
- Requires inpatient hospitalization or prolongation of existing hospitalization
- Results in persistent or significant incapacity or substantial disruption of the ability to conduct normal life functions
- Is a congenital anomaly or birth defect in an offspring of a patient taking study drug

- Is an important medical event

The term "life-threatening" refers to an event in which the patient was at immediate risk of death at the time of the event. It does not refer to an event that hypothetically might have caused death if it were more severe.

Important medical events are those that may not meet any of the criteria defined above; however, they may be considered serious when, based upon appropriate medical judgment, they may jeopardize the patient and may require medical or surgical intervention to prevent one of the other outcomes listed in the SAE definition.

Pregnancy is not considered an AE; however, information will be collected for any pregnancies that occur during the study (from the time of first dose of study drug until the final visit). Certain pregnancy outcomes will require submission as an SAE (Section 9.7.3).

The investigator is responsible for reporting to the Sponsor or its designee all AEs and SAEs that are observed or reported by the patient during the study (from the time of first dose of study drug until the final visit), regardless of their relationship to study drug or their clinical significance. All SAEs reported or observed during the study must be followed to resolution or until the investigator deems the event to be chronic or the patient to be stable. The Sponsor or its designee may contact the investigator to obtain additional information on any SAE that has not resolved at the time the patient completes the study.

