Beginning with the second 8-patient cohort, once the eighth patient enrolled completes their Week 2 visit, the DSMB will review all available safety information and recommend the dose of RTA 408 for the subsequent cohort. The DSMB dose recommendation for each cohort must not exceed 100% more than the highest dose of RTA 408 previously evaluated in this study, and the maximum permitted dose of RTA 408 is 300 mg. The dose level for each new cohort will not exceed the DSMB recommended dose level, and it will be selected by the Sponsor based on review of available safety, efficacy, PK, and PD data. Prior to opening each cohort in Part 1 for enrollment, the Sponsor will evaluate all available data from doses studied in Part 1 to determine if enough information is available to select doses for Part 2 of the study. Once enrollment begins in Part 2, no additional cohorts will be enrolled in Part 1.

Part 2: The second part of this study will be a randomized, placebo-controlled, double-blind, parallel-group study to evaluate the safety and efficacy of RTA 408 150 mg in patients with Friedreich's ataxia. Patients enrolled in Part 2 will be randomized 1:1 to receive RTA 408 150 mg, or placebo. Randomization will be stratified by pes cavus status (pes cavus vs. no pes cavus). Patients with pes cavus, a musculoskeletal foot deformity characterized by high arch of the foot that does not flatten with weight-bearing, will comprise no more than 20% of patients enrolled in Part 2. The RTA 408 dose of 150 mg was selected for Part 2 based on DSMB and Sponsor review of available data from Part 1, including safety, efficacy, PK, and PD data. Following randomization on Day 1, patients will self-administer study treatment once daily for 48 weeks. A follow-up visit for safety will occur at Week 52 (4 weeks after last dose). The DSMB will perform quarterly reviews of unblinded data for safety throughout Part 2.

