h Blood samples should be collected for hepatitis B and C and HIV antibodies only in patients lacking evidence of a negative titer in the past year.

i Negative serum pregnancy test results are required at the Screening Visit before study enrollment, and negative urine pregnancy test results are required at all other times indicated for continued participation in the study.

j A dosing diary check must be performed at study drug return and pill count.

- k Study drug should be administered in the presence of study staff in the clinic on Day 1 after all Day 1 assessments have been completed. Study drug should also be administered in the clinic on Day 14 (Visit 4), Day 84 (Visit 7), Day 168 (Visit 9), and Day 336 (Visit 13) after the blood collection for predose PK analysis. All other doses can be administered at home. Study drug should be administered once daily through Day 336 (Visit 13).
- l On study days where multiple assessments are to be completed, the maximal exercise test will be the first functional assessment performed.
- m The practice FARS assessment is not required for patients having completed a FARS assessment within 90 days prior to Screening. The practice FARS assessment must be performed prior to the screening maximal exercise test.
- n Other than the practice FARS, all FARS assessments must always be performed after the maximal exercise test.
- o Both Screening and Day 1 mFARS are required to determine patient eligibility.
- p Video of the 25-foot timed walk test is optional and will be collected only for those patients who provide consent to video.
- q Patients who consent to video collection of the 25-foot timed walk test will also have video collection during normal walking with a 25-foot (un-timed) walk using his/her normal gait. The normal walk must be performed after the 25-foot timed walk test.
- r Patients and investigators must complete the patient global impression of change and clinical global impression of change following completion of the neurological FARS exam.
- s Patients will be provided the fall diary at Screening and must record fall incidents between Screening and Week 48.
- t Blood samples for PK analysis at Day 14 (Visit 4) should be collected prior to study drug administration as well as 1, 2, 4, and 8 hours after study drug administration.

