**Table 5: Extension Schedule of Assessments**

Study Day/Week	Screening a	Day 1 b	Week 2 (telephone)	Week 4	Week 10	Week 16	Week 24 + Every 24 Weeks	End of Study
Day Relative to First Dose in Extension	-30 to -1	1	14 (±3 days)	28 (±3 days)	70 (±3 days)	112 (±3 days)	168, 336, 504, etc. (±14 days)	Within 30 days after last dose
Informed consent	X							
Inclusion/Exclusion	X	X						
Pes cavus assessment	X							
Medical history	X							
Adverse event collection		X c	X	X	X	X	X	X
Prior and Concomitant medications	X	X	X	X	X	X	X	X
Weight and BMI	X	X d		X	X	X	X	X
Vital sign measurements	X	X d		X	X	X	X	X
Physical examination	X	X d		X	X	X	X	X
Height	X			X j				
Echocardiogram e	X							
Electrocardiogram e	X							
Clinical Chemistry	X			X	X	X	X	X
Hematology	X			X	X	X	X	X
Urinalysis and microscopy	X			X	X	X	X	X
BNP and NT-proBNP f	X			X	X	X	X	X
Hepatitis B and C and HIV 	X							
Pregnancy test WOCBP h	X	X		X	X	X	X	X
Dispense study drug		X		X			X	
Study drug return and pill count				X			X	X
Neurologic FARS		X					X	X
Activities of Daily Living		X					X	X
Patient Global Impression of Change							X	
Clinical Global Impression of Change							X	
25-foot Timed Walk Test		X					X	X
9-Hole Peg Test		X					X	X

Abbreviations: BMI=body mass index; BNP= B-type natriuretic peptide; FARS=Friedreich's ataxia rating scale; HIV=human immunodeficiency virus; NT-proBNP= N-terminal prohormone of B-type natriuretic peptide; WOCBP=women of childbearing potential.

a The screening visit is only required for Part 1 patients. Assessments collected at Part 2 - Week 48 or Part 2 - Week 52 should be used to assess eligibility for Part 2 patients.

b On Day 1, all required procedures should be performed and eligibility confirmed before study drug is dispensed in the extension.

c Adverse event assessments on Day 1 should be performed following study drug administration.

d For patients enrolled in Part 2 of the study, visit procedures required at Week 52 and also Extension Day 1 should only be performed once since Part 2 Week 52 and Extension Day 1 should occur on the same day.

e For patients with echocardiograms and electrocardiograms collected within 90 days prior to the Screening Visit, the most recent echocardiogram and electrocardiogram can be used to assess patient eligibility.

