### **9.7.2. Methods of Birth Control**

From the Screening Visit, while taking study drug, and until 3 months after taking the final dose of study drug, WOCBP must agree to practice one of the following methods of birth control:

- Use of a double-barrier contraception method, defined as male use of a condom and female use of a barrier method (e.g., contraceptive sponge, spermicidal jelly or cream with or without a diaphragm)
- Use of hormonal contraceptives (oral, parenteral, vaginal, or transdermal) for at least 3 months prior to study drug administration
- Use of an intrauterine device
- Complete abstinence from sexual intercourse
- Male sterilization (with the appropriate post-vasectomy documentation of the absence of sperm in the ejaculate.) The vasectomized partner should be the sole partner for that subject.

From the Screening Visit, while taking study drug, and until 3 months after taking the final dose of study drug, males who have female partners of childbearing potential must agree to practice one of the following methods of birth control:

- Have had a vasectomy (at least 6 months earlier)
- Use of a double-barrier contraception method, defined as male use of a condom and female use of a barrier method (e.g., contraceptive sponge, spermicidal jelly or cream with or without a diaphragm)
- Partner use of hormonal contraceptives (oral, parenteral, vaginal, or transdermal) for at least 3 months prior to study drug administration
- Partner use of an intrauterine device
- Complete abstinence from sexual intercourse

Male patients must also agree to not donate sperm starting on the first day of treatment until approximately 3 months after last dose of study drug.

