### **9.7.3. Suspected Pregnancy**

During the study, all WOCBP must be instructed to contact the investigator immediately if they suspect they might be pregnant (e.g., late or missed menstrual period). Male patients must be instructed to contact the investigator if a sexual partner suspects she may be pregnant.

If a patient or investigator suspects that the patient may be pregnant, the study drug must be withheld until the results of a serum pregnancy test are available. If pregnancy is confirmed with a serum pregnancy test, the patient must discontinue taking study drug but continue to attend all study visits and undergo all study assessments. The investigator must immediately report a pregnancy associated with study drug exposure and record the event.

Pregnancy is not considered an AE; however, the investigator must follow a pregnant patient or the pregnant female partner of a male patient (if consenting) and report follow-up information regarding the course of the pregnancy, including perinatal and neonatal outcome. Infants resulting from such pregnancies should be followed for a minimum of 8 weeks. The Sponsor or its designee may contact the investigator to request additional information throughout the course of the pregnancy.

The following pregnancy outcomes must be considered SAEs and will require additional reporting in the case report form (CRF) and on an SAE form:

- Congenital anomaly/birth defect
- Stillbirth
- Spontaneous miscarriage

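### Pregnancy collection ends at the final visit, while the contraception rule runs 3 months past the last dose; for the Extension, 67% to 100% of that post-dose period has no active collection

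*Protocol*

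**What the plan says.** Three sections of the protocol bear on this.

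- **Collection window.** Section 12.2.1.2 says that information will be collected for "any pregnancies that occur during the study (from the time of first dose of study drug until the final visit".
- **Contraception window.** Section 9.7.2 starts at screening, covers treatment and continues "until 3 months after taking the final dose of study drug, WOCBP must agree to practice one of the following methods of birth control". The parallel rule for men reads "until 3 months after taking the final dose of study drug, males who have female partners of childbearing potential must agree". Male patients must also refrain from donating sperm for roughly the same time after the last dose.
- **Reporting instructions.** Section 9.7.3 opens with "During the study, all WOCBP must be instructed to contact the investigator immediately if they suspect they might be pregnant". The next sentence asks male patients to report a partner's suspected pregnancy and carries no time phrase of its own. The section also obliges the investigator to report promptly and record a pregnancy linked to study drug exposure, with no end date. Reported pregnancies are followed to outcome, and infants for at least 8 weeks.

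The schedules fix when the final visit falls. For Part 2, section 7.1 says "A follow-up visit for safety will occur at Week 52 (4 weeks after last dose" and Table 4 says "Study drug should be administered once daily through Day 336 (Visit 13". In Part 1 (Table 3) dosing ends on Day 84 and the final visit is Day 112. In the Extension (Table 5) the end-of-study visit is "Within 30 days after last dose", with no minimum interval.

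**The concern.** By asking patients to avoid conception for 3 months after the last dose, the protocol defines a post-dose period in which it thinks a pregnancy matters. The section that defines data collection stops well before the end of that period, and no schedule contains a test, call or visit after the final one.

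Safety and tolerability are a primary objective of Parts 1 and 2, and collecting ongoing safety data is part of the stated objective of the Extension. Patients were 16 to 40 years old at entry. Section 9.7.3 classes congenital anomaly, stillbirth and spontaneous miscarriage as serious adverse events. If a conception in the second or third month after the last dose is never asked about, those outcomes have no assured route into the safety record, whether the pregnancy is in a patient or in a patient's partner. The issue is completeness of safety data only; the efficacy analysis, power and type I error are not affected.

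**Working it through.** **Inputs.** Last dose: Day 84 (Part 1, Table 3) and Day 336 (Part 2, Table 4). Final visit: Day 112 (Part 1) and Day 364 (Part 2), each ±3 days; 0 to 30 days after the last dose in the Extension (Table 5). Contraception tail: 3 months (section 9.7.2), which the protocol does not convert to days. I assume 90 days and show 92 as the upper end.

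**Reproducing the plan's own figure.** Part 2: 364 − 336 = 28 days = 4 weeks, as section 7.1 states. Part 1: 112 − 84 = 28 days, the same.

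**Share of the 3-month post-dose period that lies after the final visit.** Formula: (length of 3 months − days from last dose to final visit) / length of 3 months.

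| Setting | Days covered | Uncovered, 90-day basis | Uncovered, 92-day basis |
|---|---|---|---|
| Parts 1 and 2, treatment completed, no Extension | 28 | 62/90 = 68.9% | 64/92 = 69.6% |
| Extension, visit on day 30 | 30 | 60/90 = 66.7% | 62/92 = 67.4% |
| Extension, visit on day of last dose | 0 | 90/90 = 100% | 92/92 = 100% |

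The ±3-day visit window changes little. With 3 months taken as 91 days, 31 covered days leave 60/91 = 65.9%, and 25 covered days leave 66/91 = 72.5%.

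**Who is not in this position.**

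- *Early discontinuers in Parts 1 and 2.* Section 8.5.1 asks them to complete all visits if possible. A Part 2 patient who stopped by Day 364 − 90 = Day 274 and attended Week 52 is covered for the full 90 days. In Part 1 the corresponding day is 112 − 90 = Day 22.
- *Part 2 patients who enter the Extension at Week 52.* Collection continues, and the gap moves to the end of their Extension treatment.
- *Extension patients who stop drug.* The continued-visit protection does not apply to them. Under section 9.8 they complete the end-of-study assessments and leave the study.

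**Do other passages close the gap?** The 8-week infant follow-up extends observation of pregnancies already reported, not the period in which a new one is picked up. Section 12.2.1.1 adds 30 days after the final dose for adverse events in patients who terminate early; the pregnancy sentence in 12.2.1.2 has no such addition. The investigator's undated duty in 9.7.3 could be read to cover a pregnancy that becomes known later, but it does not require the site to look for one.

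**The case against.** The strongest reply is the undated duty in section 9.7.3. A reader might infer from 12.2.1.2 that sites have no obligation at all after the final visit and that later pregnancies would simply go unreported. The documents do not support that: a pregnancy volunteered in the second or third month could be reported under 9.7.3 and followed to outcome. What remains is that the duty is passive, does not say when a pregnancy counts as linked to exposure, and stands beside an explicit cut-off in 12.2.1.2. Two sites could reasonably act differently.

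A reader might also take the two-thirds figure as a share of the whole contraception window. It is not; it is a share of the 3 months after the last dose. Measured from first dose to 91 days after the last dose, the uncovered part is 63/(336 + 91) = 63/427 = 15% in Part 2 and 63/(84 + 91) = 63/175 = 36% in Part 1. Longer Extension treatment would make it smaller still.

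Other points that stand: the protocol never states that reproductive risk persists for 3 months, which is an inference from a precaution; no passage requires the two windows to match; and ending pregnancy collection at the final visit broadly agrees with the adverse event window. Consent pages are not in the review copy and the Investigator's Brochure was not available, so instructions to patients after the study could exist there. Finally, Appendix 13 states that Parts 1 and 2 were already complete, so no edit can change what was collected in them.

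**Conclusion.** The mismatch is real and worth correcting, as an inexpensive improvement to safety data rather than a flaw that threatens the trial's conclusions. As written, active pregnancy collection ends 28 days after the last dose for patients who completed treatment in Part 1 or 2 and did not enter the Extension, leaving about 69% of the 3-month post-dose period outside it. It ends 0 to 30 days after the last dose in the Extension, leaving 67% to 100%. Patients who stopped drug early in Part 1 or 2 but kept attending may be fully covered.

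These figures rest on 3 months being 90 days and on visits at their scheduled times. They describe time without active collection, not pregnancies missed: the documents give no basis for an expected number, and patients have agreed to contraception for exactly those months. The conclusion is about the protocol text alone.

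**What to change.** Reconcile sections 9.7.2, 9.7.3 and 12.2.1.2 for the Extension, the only part still able to benefit:

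- In 12.2.1.2, end pregnancy collection 3 months after the final dose of study drug instead of at the final visit, for patients and for consenting female partners of male patients.
- In 9.7.3, give the reporting instructions for women and for men the same end date, and say that the investigator's duty to report runs at least as long.
- At the end-of-study visit, tell patients to report a pregnancy up to that date.
- If the sponsor accepts it, add one telephone contact at 3 months for women of childbearing potential and for men with partners of childbearing potential.

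This uses the protocol's own 3-month figure and changes no dose, contraception rule or treatment decision. It costs a sentence in each of two sections, a reminder at a visit already scheduled, and at most one call per affected patient. The downside is that pregnancy data close slightly later.

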### **12.3. Eliciting Adverse Event Information**

At every study visit, patients must be asked a standard, non-directed question, such as, "How do you feel?" or "How have you been feeling since your last visit?" to elicit any medically related changes in their well-being. They will also be asked if they have been hospitalized, had any accidents, used any new medications, or changed concomitant medication regimens (including prescription drugs, over-the-counter medications, vitamins, herbal products, and minerals). Responses should be recorded in the source documents.

In addition to patient observations, AEs must be documented for any clinically significant diagnosis resulting from abnormal laboratory test values, physical examination findings, ECG abnormalities, or other documents that are relevant to patient safety.

### **12.4. Assessment of Causality**

The investigator must use the following classifications and criteria to characterize the relationship or association of the study drug in causing or contributing to the AE:

- Unrelated: This relationship suggests that there is no association between the study drug and the reported event.
- Unlikely: This relationship suggests that the temporal sequence of the event with study drug administration makes a causal relationship improbable and/or other factors also provide plausible explanations.
- Possible: This relationship suggests that treatment with the study drug caused or contributed to the AE. That is, the event follows a reasonable temporal sequence

from the time of study drug administration and/or follows a known response pattern to the study drug but could have been produced by other factors.

- Probable: This relationship suggests that a reasonable temporal sequence of the event with study drug administration exists and, based upon the known pharmacological action of the drug, known or previously reported adverse reactions to the drug or class of drugs, or judgment based on the investigator's clinical experience, the association of the event with study drug administration seems likely.

## 12.5. Assessment of Severity

The investigator will grade the severity of the AEs as mild, moderate, or severe using the following definitions:

- Mild: Symptoms causing no or minimal interference with usual social and functional activities
- Moderate: Symptoms causing greater than minimal interference with usual social and functional activities
- Severe: Symptoms causing inability to perform usual social and functional activities

## 12.6. Recording Adverse Events

All conditions present prior to the first dose of study drug should be documented as medical history. All drug-related (characterized as possibly or probably related; Section 12.4) AEs and abnormal laboratory test results reported or observed during the study must be followed to resolution (either return to baseline or within normal limits). All other AEs or non-drug-related abnormal laboratory results will be followed through the final visit (i.e., end of study or early termination). Information to be collected includes type of event, date of onset, date of resolution, investigator-specified assessment of severity and relationship to study drug, seriousness, as well as any action taken.

While an AE is ongoing, changes in the severity (e.g., worsening or improving) should be noted in the source documents but when documenting the AE, only the total duration and greatest severity should be recorded in the CRF. AEs characterized as intermittent require documentation of onset and duration.

AEs resulting from concurrent illnesses, reactions to concurrent illnesses, reactions to concurrent medications, or progression of disease states must also be reported. Pre-existing conditions (present before the start of the AE collection period) are considered concurrent medical conditions and should NOT be recorded as AEs. However, if the patient experiences a worsening or complication of such a concurrent condition, the worsening or complication (except disease progression) should be recorded as an AE. Investigators should ensure that the AE term recorded captures the change in the condition (e.g., "worsening of...").

Each AE should be recorded to represent a single diagnosis. Accompanying signs (including abnormal laboratory test values or ECG findings) or symptoms should NOT be recorded as additional AEs. If a diagnosis is unknown, sign(s) or symptom(s) should be recorded as an AE(s). Changes in laboratory test values or ECG parameters are only considered to be AEs if they are judged to be clinically significant (i.e., if some action or intervention is required or if the

investigator judges the change to be beyond the range of normal physiological fluctuation). If abnormal laboratory test values or ECG findings are the result of pathology for which there is an overall diagnosis (e.g., increased creatinine levels in renal failure), only the diagnosis should be reported as an AE.

Elective procedures (surgeries or therapies) that were scheduled prior to the start of AE collection are not considered AEs. These elective procedures should not be recorded as AEs but should be documented in the patient's source documents as elective (e.g., elective periodontal surgery). However, if a preplanned procedure is performed early (e.g., as an emergency) because of a worsening of the pre-existing condition, the worsening of the condition should be captured as an AE.

